## 8.3. Second Intermediate Evaluation (T2 at 60 days)

Both for the experimental and control group, participants will be checked by investigator firstly if they were re-admitted in the hospital after 60 days of system utilization. The investigator will conduct interview for clinical resource utilization and evaluate level of quality of life through VAS and physical condition using the SPPB.

## 8.4. Final evaluation (T3 at 90 days)

At the end of the trial, both experimental and control group participants are checked if they went into a rehospitalization after 90 days of system utilization. The investigator will conduct interview for clinical resource utilization, self-management improvement and effectiveness of the system by administering questionnaires and interviews, along with an evaluation of the level of quality of life through VAS and of the physical condition using the SPPB. Moreover, the investigator will evaluate usability of platform and system using SUS, the health-related quality of life using the SF-12 and the eHealth literacy using the eHEALS.

Finally, the devices including tablet, medical and non-medical devices will be withdrawn.

# 9 Data analysis

- Sample size: The study by O'Connor et al. (2023) [30], in which a remote monitoring and tele-health system was tested for the prevention of 30-day re-hospitalization in older patients with heart failure, was taken as a reference to calculate the sample size and statistical power of the study. The research, comparing two groups, one intervention and one control group, as in the case of the TransCare project, showed that the rate of re-admission to the hospital at 30 days (primary endpoint) in the intervention group was 5.2 % while in the control group was 19.3 %. Now, assuming a 14.1 % reduction in 30-day re-hospitalization rates by remote monitoring intervention, and considering a power analysis based on two independent groups (two-tail Fisher's exact test) with an error α =0.05 and  $P = (1 - \beta \text{ prob. err.}) = 0.85,$ probability а statistical power then a sample of 206 participants, equally allocated with ratio 1/1 in 103 in the intervention group and 103 in the control group, can be sufficient to be considered clinically valid in the pilot trial of TransCare project experimentation.
- Data collected by the researchers: The first step of the data analysis will deal with the description of • the sample. Continuous variables will be reported as either mean and standard deviation or median and interquartile range based on their distribution (assessed using Kolmogorov-Smirnov test). Categorical variables will be expressed as an absolute number and percentage. Comparison of baseline measurements between groups will be evaluated by unpaired t-test (for normal distribution), Mann-Whitney U tests (for non-normal distribution), or Chi-Square tests (for categorical variables). Within each group, independent and dependent variables will be compared between the pre- and post- conditions using the same tests as appropriate. The treatment effect on the outcome variables will be evaluated by using repeated measures ANOVA, to compare the changes over time in the outcome measures between the intervention group and the control group. Moreover, a linear regression model on the outcome variation between baseline and follow-up will be estimated to evaluate the effect of the treatment adjusted for all potential confounders. Descriptive statistical analyses will be performed on the quantitative data with SPSS or Rstudio. All data acquired in the trial will be analysed directly by the research centres involved in the project consortium. Monitored data will be used as input to the ML-based post discharge analytics for training and inference processes allowing for the prediction of different parameters among patients involved in the experimentation. The ML component will determine insights that can be used as support by medical professionals to identify the problems that require proactive intervention. Work will be done on anonymized data and not on personal data, and the AI model will not interact for the testing phase with the end user, be it the patient or the practitioner. The practitioners can only access the results of the ML inference for their remotely monitored patients and to visualize the results in order to support their decisions regarding patients' treatment.
- Data collected by the technological devices: One of the uses of the data collected from the medical devices is to infer the rehospitalization rate of the user and to know. The aggregation of activity data from several testing center will serve also to the researcher to pool a data lake to train predictive machine learning model for further implementation in the re-hospitalization field. The analysis of user activity data and their interactions at well-defined milestones in the experiment will make it possible to detect system failures as early as possible, in order to prevent the user from dropping out. All the data will be treated in anonymized during processing and analysis.

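### Within-group pre/post comparisons are sent to tests for independent samples, although the two values come from the same participants

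*Protocol*

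**What the plan says.** The analysis paragraph of protocol section 9 takes four steps.

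- Baseline comparison between groups: "Comparison of baseline measurements between groups will be evaluated by unpaired t-test (for normal distribution), Mann-Whitney U tests (for non-normal distribution), or Chi-Square tests", the last for categorical variables.
- Pre/post comparison within each group: "independent and dependent variables will be compared between the pre- and post- conditions using the same tests as appropriate".
- Treatment effect: "evaluated by using repeated measures ANOVA, to compare the changes over time in the outcome measures between the intervention group and the control group".
- In addition, "a linear regression model on the outcome variation between baseline and follow-up will be estimated", in order to "evaluate the effect of the treatment adjusted for all potential confounders". The confounders are not listed.

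Table 5 in section 7 repeats four scales on the same participants: SPPB at R, T1, T2 and T3; EQ VAS at T0, T1, T2 and T3; SF-12 and eHEALS at T0, T1 and T3. Section 8.1 says that controls receive no technology and are only checked for re-hospitalization. Section 8.2 limits the T1 scale assessments to the experimental group.

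**The concern.** The second step borrows its tests from the first. In the first step the two samples are different people, so independent-sample tests are right. In the second they are the same people measured twice, so those tests are wrong: they discard the within-person correlation, and the standard errors and p-values do not describe the comparison being made.

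What is at stake is real change on SPPB, EQ VAS, SF-12 or eHEALS going undetected. If the text of sections 8.1 and 8.2 governs, there are no control values for SPPB and EQ VAS at T1. The pre/post comparison in the experimental arm would then be the only test available for those scales at that visit.

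A smaller matter sits beside it. The regression on change does not say that the baseline value of the outcome is a covariate, although that value is collected.

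**Working it through.** **The plan's own figure.** Section 9 sizes the trial on the binary 30-day endpoint with Fisher's exact test: "considering a power analysis based on two independent groups (two-tail", "with an error α =0.05", power 0.85, rates 5.2% and 19.3%, giving 103 per arm. Exact enumeration of the two-sided Fisher test gives power 0.849 at 102 per arm and 0.852 at 103 per arm. The stated 2 x 103 = 206 is reproduced. It uses no pre/post comparison, so nothing below changes it.

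**Inputs.** Two-sided alpha 0.05 is from section 9. The pre/post correlation rho is not in the protocol and is assumed, from 0.3 to 0.8. Pre and post variances are taken as equal (sigma^2), with n participants and a normal approximation. The 80% reference power is for illustration only.

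**Standard error.** For the mean change:

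- paired: variance = 2 sigma^2 (1 - rho) / n
- treated as independent: variance = 2 sigma^2 / n
- ratio of standard errors, unpaired to paired = 1/sqrt(1 - rho)

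**True type I error** of the unpaired test at nominal 5% = 2[1 - Phi(1.960 / sqrt(1 - rho))].

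**Power** of the unpaired test where the paired test has 80% = Phi((1.960 + 0.842) sqrt(1 - rho) - 1.960).

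Example at rho = 0.5: sqrt(0.5) = 0.707. The SE ratio is 1/0.707 = 1.41. The type I error is 2[1 - Phi(2.772)] = 0.0056. The power is Phi(2.802 x 0.707 - 1.960) = Phi(0.021) = 0.508.

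| Assumed rho | SE ratio | True type I error | Power (paired = 80%) |
|---|---|---|---|
| 0.3 | 1.20 | 1.9% | 65% |
| 0.5 | 1.41 | 0.56% | 51% |
| 0.7 | 1.83 | 0.03% | 34% |
| 0.8 | 2.24 | 0.001% | 24% |

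These figures are for comparisons of means. Mann-Whitney U and Chi-Square rest on the same independence assumption, but their exact loss is not computed here.

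**Baseline value in the change regression.** Per participant, the unadjusted change has variance 2 sigma^2 (1 - rho). After adjustment for baseline, the residual variance is sigma^2 (1 - rho^2). The ratio is (1 - rho^2) / [2(1 - rho)] = (1 + rho)/2, which is 0.65, 0.75, 0.85 and 0.90 at rho = 0.3, 0.5, 0.7 and 0.8.

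**The case against.** The strongest reply is that the sentence ends with a qualifier leaving the choice of test to what suits the data, and that a competent analyst would use paired versions. The next sentence also plans a repeated measures ANOVA, which does respect within-person correlation. Part of this stands: the authors may well have meant paired tests, and the treatment effect itself does not rest on the faulty sentence. But the qualifier can only choose among the tests already named, and none of them is paired. This is a method stated wrongly, not a detail left to the SAP.

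A second reply is that the harm is limited. That stands in full. The error makes the tests too cautious, and within-group tests do not estimate the treatment effect.

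Three stronger readings are tempting, and the protocol does not support them.

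- A reader might infer that the ANOVA leaves out the baseline value. It does not: it compares changes over time, so baseline enters as one of the time levels.
- A reader might infer that the change-score regression is invalid. In a randomised comparison an unadjusted change score is valid, only less efficient and more exposed to chance imbalance at baseline. The unlisted confounders might also include the baseline value.
- A reader might infer that patients with a missed visit will be dropped and the scale results biased. Classical repeated measures ANOVA does need every visit, but the protocol neither prescribes a complete-case analysis nor gives a missed-visit rate. The abandonment mentioned in section 10 is of the technology, not of assessments. Handling of missing data may properly be left to the SAP.

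**Conclusion.** The point holds for the within-group sentence. As written, it applies independent-sample tests to repeated measurements on the same participants. For an assumed pre/post correlation of 0.3 to 0.8, standard errors are 1.20 to 2.24 times too large, and 80% power falls to between 65% and 24%. The direction depends on the correlation being positive, which is expected when the same scale is repeated on the same person. There is no excess of false positives.

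The scope is the within-group results for SPPB, EQ VAS, SF-12 and eHEALS, all secondary. The primary endpoint is binary and has no pre value, so it is unaffected, as is the sample size.

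Stating the baseline covariate is a recommended improvement. At assumed correlations of 0.5 to 0.7, adjustment brings the variance to 75% to 85% of that of the unadjusted change score.

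Separately, the planned two-group ANOVA conflicts with sections 8.1 and 8.2. If controls have no scale values at T1, no model can estimate the difference between arms at that visit.

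**What to change.** 1. In section 9, replace the reference back to the same tests with named paired tests: paired t-test or Wilcoxon signed-rank for the scales, and McNemar for paired binary variables. Label all within-group results as descriptive.
2. State that the linear regression on change includes the outcome's own baseline value (R for SPPB; T0 for EQ VAS, SF-12 and eHEALS) as a covariate.
3. Reconcile sections 8.1 and 8.2 with Table 5 and with the two-group ANOVA, stating for each scale and visit whether controls are assessed.

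Items 1 and 2 change wording only: no new data, no change in sample size, and standard procedures in R and SPSS. Item 3 costs only wording if controls are already meant to be assessed. If they are not, either control assessments are added, which is extra fieldwork, or the affected between-group comparisons are withdrawn.

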# **10 Risk-benefit analysis**

The user may be faced with a technological environment that he/she cannot fully manage or understand. This may generate frustration in the user and drive him/her to abandon it. However, the researchers involved will do training when the devices are installed on their use, functions, and all the risks associated with utilization.

It is also expected that there is a low risk that the user could get hurt with the proposed tools.

Indeed, the hardware devices used are commercial devices and CE certified and/or safety certification, the applications for older people and caregivers will be loaded on the hardware held by the users. Technological dependence represents a major ethical dilemma today and scientific community. To limit the risk, the European Commission's international programmes have introduced guidelines for conducting studies that require the introduction of a new technology, called Responsible Innovation. The core principles of Responsible Innovation are also applied within the TransCare project. A strategy underlying the prevention of technological dependence is the inclusion of different actors around the older people, in the process of acquiring skills and daily use of technology. In this way, technological solutions such as those proposed by TransCare, respond to the definition of socio-technological system that does not expect to replace of the caregiver and the health professionals but stimulates the user to play a leading role in the management of their health. The services proposed are intended to support the post-discharge home monitoring and do not replace (in whole or in part) the support from professional services. During the installation of the technology, moreover, information will be provided to the participants and their caregiver about the limits of the technology. Users who take part in the study will not incur any direct or indirect costs related to the use of the technology platform. The platform will be provided to the subjects by the experimental sites and must be returned to the research team at the end of the trial.

# 11 Data management

The project committed to the maintenance of participants' anonymity and confidentiality throughout all procedures, including screening, recruitment, testing, evaluation and dissemination procedures. Data collection, usage and storage procedures complied with national laws and the EU's General Data Protection Regulation (GDPR) including the commitment of participants' the right to access, right to be informed, right to withdraw, and right to data erasure. Moreover, the servers are in the European Union and compliant to GDPR. Data collection will be compliant with the principle of data minimization i.e. the collection of personal information from study participants will be limited to what is directly relevant and necessary to accomplish the specific goals of the testing and evaluation work packages. Data entry will be carried out using specific software, providing blocks and data entry checks, to reduce the number of entry errors. All screening data will be discarded upon the project completion. During the testing procedures have been completed. Anonymized research data shall be made openly available for secondary analysis from 5 to 10 years after the project completion. A more detailed data management plan is annexed in deliverable D3.3 that deals with ethics and privacy procedures.

# 12 Legal and technical aspects

The study will be conducted considering regulatory requirements and legal requirements, and the study will be initiated following receipt of an evaluation and approval of the study by an independent Ethics Committee and completion of the administrative requirements of the institution where the study is being conducted.

In addition, all potentially eligible participants will be required to receive complete information about the study and provide their consent to participate in the study. Moreover, participant must provide consent to the processing of personal data in anonymous and aggregate form, in accordance with EU Regulation 2016/679 (GDPR) on the protection of individuals regarding the processing of personal data and Legislative Decree No. 101/2018 - Provisions for the adaptation of national legislation to the provisions of European Regulation 2016/679.

Then, the participant must be informed that his or her data may be examined by authorized personnel or by members of the competent ethics committee and officials of the competent regulatory authorities. Finally, the participant is also informed and asked to provide ad hoc informed consent to participate in the study, including data retention for up to 10 years after completion of the study.

Each signature must be personally dated by each signatory, and the informed consent and any additional patient information must be retained by the investigator. A signed copy of the informed consent and information sheet will be given to each patient, or their informal caregiver or legal tutor, should they be unable to independently give their signed informed consent.

The Participant can indicate his or her agreement to the retention and use of his or her data long after the end of the project under the open access to scientific publications and open research data as requested by the European Commission.

# **APPENDIX**

Socio-Demographic Data

ID patient \_\_\_\_\_ Date

Date of birth (dd /mm /yyyy)	(dd /mm /yyyy)/				
Gender	🗆 male 🛛 female 🗆 diverse				
Residence	City     Suburban     Rural community				
Housing situation	
 
Alone  Grad Shared apartment  Grad Family
 
With (marriage) partner  Grad Other:
 
				
Marital status	
 
Single  widowed  divorced
 
married / registered civil partnership  solid
 
partnership
 
				
Do you have children?	□ no □ yes $\rightarrow$ if yes, how many:				
Do you have grandchildren?	□ no □ yes $\rightarrow$ if yes, how many:				
Highest level of education	
 
No school degree
 
Primary school
 
Secondary school
 
High school
 
University degree
 
				
Currently employed	
 
no
 
yes → if yes, please mark where applicable:
 
Part-time □ Minijob □ Full-time
 
				

Currently retired	🗆 no	□ yes
	ightarrow if yes, si	nce when (year):
Able to stand and walk even with support	□ no	□ yes
Use of active implant or not-implant medical devices	□ no	□ yes
Pacemaker or implantable cardioverter defibrillator	no no	□ yes
Allergy to nichel components	□ no	□ yes
A myocardial infarction or stroke within 1 months	□ no	□ yes
Metastatic cancer or immunosuppressive therapy	no no	□ yes
Mini Mental State Examination	SCORE:	
Clinical Frailty Scale	SCORE:	

RECRUITMENT

Mini Mental State Examination (MMSE)

# Mini-Mental State Examination (MMSE)

Patient's Name:

Date:

Instructions: Ask the questions in the order listed. Score one point for each correct response within each question or activity.

Maximum Score	Patient's Score	Questions
5		"What is the year? Season? Date? Day of the week? Month?"
5	s.	"Where are we now: State? County? Town/city? Hospital? Floor?"
3		The examiner names three unrelated objects clearly and slowly, then asks the patient to name all three of them. The patient's response is used for scoring. The examiner repeats them until patient learns all of them, if possible. Number of trials:
5		"I would like you to count backward from 100 by sevens." (93, 86, 79, 72, 65,) Stop after five answers. Alternative: "Spell WORLD backwards." (D-L-R-O-W)
3		"Earlier I told you the names of three things. Can you tell me what those were?"
2		Show the patient two simple objects, such as a wristwatch and a pencil, and ask the patient to name them.
1	14	"Repeat the phrase: 'No ifs, ands, or buts.'"
3		"Take the paper in your right hand, fold it in half, and put it on the floor." (The examiner gives the patient a piece of blank paper.)
1		"Please read this and do what it says." (Written instruction is "Close your eyes.")
1		"Make up and write a sentence about anything." (This sentence must contain a noun and a verb.)
1		"Please copy this picture." (The examiner gives the patient a blank piece of paper and asks him/her to draw the symbol below. All 10 angles must be present and two must intersect.)
30		TOTAL

(Adapted from Rovner & Folstein, 1987)

# Clinical Frailty Scale (CFS)

1	ţ	Very Fit - People who are robust, active, energetic and motivated. These people commonly exercise regularly. They are among the fittest for their age.
2	Ţ	Well - People who have no active disease symptoms but are less fit than category 1. Often, they exercise or are very active occasionally, e.g. seasonally.
3	t	Managing Well - People whose medical problems are well controlled, but are not regularly active beyond routine walking.
4	1	Vulnerable - While not dependent on others for daily help, often symptoms limit activities. A common complaint is being "slowed up", and/or being tired during the day.
5		Mildly Frail - These people often have more evident slowing, and need help in high order IADLs (finances, transportation, heavy housework, medications). Typically, mild frailty progressively impairs shopping and walking outside alone, meal preparation and house work.
6		Moderately Frail - People need help with all outside activities and with keeping house. Inside, they often have problems with stairs and need help with bathing and might need minimal assistance (cuing, standby) with dressing.
7	, A	Severely Frail - Completely dependent for personal care, from whatever cause (physical or cognitive). Even so, they seem stable and not at high risk of dying (within $\sim 6$ months).
8		Very Severely Frail - Completely dependent, approaching the end of life. Typically, they could not recover even from a minor illness.
9	6	Terminally III - Approaching the end of life. This category applies to people with a life expectancy < 6 months, who are not otherwise evidently frail.

#### Short Physical Performance Battery

#### 1. Repeated Chair Stands

Instructions: Please **stand up straight as quickly as you can five times, without stopping in between**. After standing up each time, sit down and then stand up again. Keep your arms folded across your chest. Please watch while I demonstrate. I'll be timing you with a stopwatch. Are you ready?

Begin Grading: **Begin stop watch when subject begins to stand up**. Count aloud each time subject arises. **Stop the stopwatch when subject has straightened up completely for the fifth time**. Also stop if the subject uses arms, or after 1 minute, if subject has not completed rises, and if concerned about the subject's safety. Record the number of seconds and the presence of imbalance.

- Time: \_\_sec (if five stands are completed)
- Number of Stands Completed: 1 2 3 4

5 Chair Stand Ordinal Score:

- 0 = unable
- 1 = > 16.7 sec
- 2 = 16.6-13.7 sec
- 3 = 13.6-11.2 sec
- 4 = < 11.1 sec

#### 2. Balance Testing

Begin with a **semitandem stand** (heel of one foot placed by the big toe of the other foot). Individuals unable to hold this position should try the side-by-side position. Those able to stand in the semitandem position should be tested in the full tandem position. Once you have completed time measures, complete ordinal scoring.

